## 6.1. Exclusion criteria

Adherence to criteria specified in the protocol is essential. Exclusion criteria deviations are not allowed because they can potentially jeopardize the scientific integrity or regulatory acceptability of the study or safety of the participant. The following criteria should be checked at the time of study entry.

Potential participants must not be included in this trial if any of the following exclusion criteria applies:

- Individuals who are medically immunocompromised (definition of medications as separate list), less than 2 years since hematopoietic stem cell transplantation (HSCT) or graft-versus-host disease (GVHD), solid-organ transplanted, other immunosuppressive drugs for treatment of cancer and inflammatory mediated or autoimmune conditions e.g. TNF-inhibitors, anti-CD20 drugs, IL-inhibitors, methotrexate, cytostatics etc., as judged by the investigator.
- Individuals who have already received an RSV vaccine dose at any time in the past.
- Any known or suspected reaction, hypersensitivity or allergies to be exacerbated by any product or component included in the vaccine and

trial.

- Mental inability, reluctance or language difficulties that result in difficulty understanding the meaning of participation in the trial.
- Treatment or disease which, according to the investigator, can affect treatment or trial results. However, if a participant begins a treatment during the study that could affect the immune system, they will not be discontinued from the study. In such cases, the details of the treatment will be documented appropriately. The participant will be followed for safety until the end of the safety follow-up period. If the participants continue the study, they will also receive the revaccination at one year.
- Any of the following medical conditions:
  - Unstable chronic illness
  - Recurrent or un-controlled neurological disorders or seizures.
  - Significant underlying illness that in the opinion of the investigator would be expected to prevent completion of the study.
  - Any other medical condition that in the judgment of the investigator would make intramuscular injection unsafe
  - Any other clinical condition that, in the opinion of the investigator, might pose additional risk to the participant due to participation in the study.
  - Any history of dementia or any medical condition that moderately or severely impairs cognition and understanding of the informed consent form and/or study procedures.
  - History of chronic alcohol consumption and/or drug abuse as deemed by the investigator to render the potential participant unable/unlikely to provide accurate safety reports or comply with study procedures.

- Planned move during the study period that will prohibit participating in the

study until study end.

- Participation of any study personnel or their immediate dependents, family or household members as well as any family relations to sponsor or PI.
- Co-administration of other vaccines less than 14 days before or after study vaccination. A period of less than 30 days before or after study vaccination applies in the case of Shingrix.

## **6.2. Screening and inclusion**

Participant eligibility (that participants fulfil all inclusion criteria and do not meet any exclusion criteria) is established at baseline visit before visit 1, or if these two visits are at the same time, before deciding to give the first dose of the study vaccine.

Study vaccine administration may be postponed within the permitted timeframe for each study vaccination if a possible candidate cannot receive the vaccine at the baseline visit. Vaccination can be delayed for 10 days in case of:

- Acute disease and/or fever at the time of vaccination. Fever is defined as a temperature  $\geq 38.0^{\circ}\text{C}/100.4^{\circ}\text{F}$  by any route. The route for measuring temperature can be oral, axillary or tympanic.

Participants with a minor illness (such as mild diarrhea, mild upper respiratory infection) without fever may be vaccinated at the discretion of the investigator.

## **6.3. Withdrawal criteria**

Participants can discontinue their participation in the trial at any time without any consequence to his/her continued treatment. The investigator/sponsor can at any time terminate the trial for a participant due to, e.g., unacceptable AEs/ARs or because the participant does not follow the procedures in the clinical trial protocol.

If a participant prematurely discontinues the trial, a safety follow-up visit will be performed (at 6 months following prime vaccination or revaccination). If the participant does not want to attend the follow-up visit or if it is not possible to establish contact, this will be recorded.

No replacement of discontinued participants will be done. Data from participants who discontinue the trial prematurely can be included in the analysis, provided the participant has given consent for such use.

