## List of used acronyms and abbreviations

Abbreviation	Term/Explanation
AE	Adverse Event = Any untoward medical occurrence in a participant to whom a medicinal product is administered and which does not necessarily have a causal relationship with this treatment.

SAE	Serious Adverse Event = Any untoward medical occurrence that at any dose requires inpatient hospitalisation or prolongation of existing hospitalisation, results in persistent or significant disability or incapacity, results in a congenital anomaly or birth defect, is life-threatening, or results in death
AESI	Adverse Events of Special Interest
AR	Adverse Reaction = any unfavourable and unintended reaction to an investigational medicinal product, regardless of dose
ASR	Annual Safety Report = the annual safety report for reporting to authorities. In Sweden this is the Swedish Medical Products Agency via CTIS.
ATCC	American Type Culture Collection
BCR	B cell receptor
CA	Competent Authorities
CD	Cluster of Differentiation
CFS	Clinical Frailty Scale
CIOMS	Council for International Organizations of Medical Sciences
CMI	Cell-mediated immunity
CRF/eCRF	Case Report Form/electronic Case Report Form
CTIS	Clinical Trials Information System = Centralized EU database/portal for application and communication with authorities concerning clinical trials. In Sweden this includes the Swedish Medical Products Agency and the Swedish Ethical Review Authority.
CTR	EU Regulation 536/2014, also called CTR, Clinical Trials Regulation
DOPC	Dioleoyl phosphatidylcholine
DSUR	Development Safety Update Report = the standard which should be used for annual safety reporting to authorities
ELISA	Enzyme-linked immunosorbent assay

EMA	European Medicines Agency
EU/EEA	European Union/European Economic Area
FACS	Fluorescence-activated cell sorting
FDA	Food and Drug Administration
GCP	Good Clinical Practice
GDPR	General Data Protection Regulation
GMT	Geometric mean titer
GSK	GlaxoSmithKline Biologicals S.A.
GVHD	Graft-versus-host disease
HSCT	Hematopoietic stem cell transplantation
IB	Investigator's Brochure
ICF	Informed Consent Form
ICH	International Council for Harmonization
IgG	Immunoglobulin G
IL	Interleukin
ITT	Intention-to-treat = including all data from all participants who have participated in the trial
Läkemedelsverket	Swedish Medical Products Agency – the national authority responsible for regulation and surveillance of the development, manufacturing and sale of medicinal products.
LFF	Läkemedelsförsäkringen

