LÖF	Landstingens Ömsesidiga Försäkringsbolag
LRTD	Lower Respiratory Tract Disease
mAb/Ab	Monoclonal antibody/Antibody
MGI	Mean geometric increase

Member State	European Union (EU) Member state where an application for authorisation of a clinical trial or of a substantial modification has been submitted.
MPL	3-O-desacyl-4'-monophosphoryl lipid A
mRNA/RNA	Messenger ribonucleic acid/ribonucleic acid
N/A	Not applicable
PBMC	Peripheral blood mononuclear cell
PI	Principal Investigator
pIMD	Potential immune-mediated disease = autoimmune diseases and other inflammatory and/or neurologic disorders which may or may not have an autoimmune etiology
postF	Postfusion
PP	Per Protocol analysis = including only data from participants who have completed the trial in accordance with the protocol, with no deviations from the protocol
preF	Prefusion
RSI	Reference safety information = A list of all known serious adverse reactions for the investigational medicinal product, including severity and frequency of the adverse reaction. The RSI is contained in the Summary of Product Characteristics or IB and is used to determine which adverse reactions should be reported as suspected unexpected serious adverse reactions (SUSARs).
RSV	Respiratory syncytial virus
RSVPreF3	Vaccine antigen; recombinant RSV glycoprotein F stabilized in pre-fusion conformation
SAP	Statistical Analysis Plan
SOP	Standard Operating Procedure
SPC or SmPC	Summary of Product Characteristics
SUSAR	Suspected Unexpected Serious Adverse Reaction = This is an event that is likely related to the investigational medicinal product but with unexpected occurrence. An adverse reaction is

	unexpected if its nature or seriousness is not consistent with the information on the product in the RSI.
Tfh	T follicular helper cell
TMB	3,3 ,5,5 -Tetramethylbenzidine
TNF	Tumor necrosis factor
US	United States
USM	Urgent Safety Measures
VE	Vaccine efficacy

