#### ***8.1.1. Methods for the primary endpoint***

The primary endpoint of this trial is defined as the descriptive analysis of the differences in RSV A and B neutralizing antibodies at D31 after prime vaccination in the two age groups enrolled in this study. The primary endpoint will be measured in serum by an established neutralization assay. The assays will be performed at accredited laboratories of GSK. The analysis will be performed after the collection of all D31 samples. A short description of the method can be found in section 16.

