## **10. Statistics**

### **10.1. Analysis population**

The trial intends to include all participants into the analysis for the primary endpoint. A primary per-protocol analysis will be performed and can be complemented by a secondary analysis including all enrolled participants that have received at least one dose of Arexvy.

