### **10.2.2. *Drop-outs***

A 10-20% of dropouts in the older adult cohort (80+ years) is expected during the study based on previous experience. Enrollment of participants will therefore intend to account for this, including 65-70 participants in total, with 30 participants in the 60-65 years age group and 35-40 participants in the 80+ older adult cohort. The extent of missing data will be reported.

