### **10.4. *Sample size calculations***

This study is primarily designed to gather descriptive immunogenicity data in older adults upon vaccination with Arexvy, including adults of 80 years of age and older for which data is currently limited. As the study objective is purely descriptive rather than to demonstrate efficacy or test a hypothesis, no formal power-based sample size calculation has been made.

A sample size of 30 individuals in the 60-65 years group and of 35-40 individuals in the 80+ years group was chosen based on feasibility of recruitment, clinical judgement and a 10-20% drop-out expected in the older age group. This sample size of approximately 30 individuals per age group is expected to generate valuable immunogenicity data in an otherwise understudied population and to allow for exploratory comparisons between age groups. Given the descriptive nature of the study, its findings will be interpreted as preliminary.

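### Section 6.3 makes use of leavers' collected data optional and subject to an undefined consent, at odds with the all-participant intent of section 10.1

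*Protocol*

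**What the plan says.** - **Protocol 6.3 (Withdrawal criteria)** gives the rule for leavers in both age groups: "Data from participants who discontinue the trial prematurely can be included in the analysis, provided the participant has given consent for such use". It names no criterion, no decision-maker and no time of decision. It does not say which consent is meant, or whether the rule covers immunogenicity, safety or both.
- **Protocol 10.1 (Analysis population)** opens with a different aim: "The trial intends to include all participants into the analysis for the primary endpoint". It then says: "A primary per-protocol analysis will be performed and can be complemented by a secondary analysis including all enrolled participants". The complementary set is limited to those who received the vaccine.
- **List of acronyms and abbreviations** defines per-protocol as "including only data from participants who have completed the trial in accordance with the protocol, with no deviations from the protocol". It defines intention-to-treat as "including all data from all participants who have participated in the trial", but section 10 names no set by that term.
- **Protocol 8.1.1** fixes when the primary endpoint is analysed: "The analysis will be performed after the collection of all D31 samples". Section 10.5 gives the same timing.
- **Protocol 10.2.2** states: "A 10-20% of dropouts in the older adult cohort (80+ years) is expected during the study based on previous experience". No rate is given for the younger group. Section 10.4 gives the group sizes: "A sample size of 30 individuals in the 60-65 years group and of 35-40 individuals in the 80+ years group was chosen".
- **Protocol 10.2.1** reports safety as counts and percentages in each age group.

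**The concern.** A participant who leaves at month 4 has a day 31 titre as valid as anyone else's, and an adverse event recorded before leaving is still an event in a vaccinated person. Whether such data are analysed should be settled before anyone leaves. Section 6.3 leaves it open twice: by wording inclusion as a possibility, and by attaching a consent condition without saying where or when that consent is given.

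Three features of this trial make the gap more than editorial. It is open-label, and section 7.1.5 says the sponsor's laboratory staff know the age group through the site. Discontinuation can depend on outcome, because 6.3 itself lets the investigator or sponsor end participation for unacceptable adverse events. Results are analysed in stages (10.5), so a later decision about a leaver's data could be taken with day 31 results already known. At stake are the descriptive GMT, MGI and sero-response figures and the safety percentages, above all in the group aged 80 or over, which the trial was set up to describe.

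**Working it through.** **1. The plan's own figure.** Section 10.4 aims for about 30 people per age group and allows for 10-20% drop-out in the older one. Enrolment needed = 30 / (1 − d), rounded up:
- d = 0.10: 30 / 0.90 = 33.3, so 34
- d = 0.20: 30 / 0.80 = 37.5, so 38

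The stated 35-40 agrees to within 2. There is no power calculation to reproduce, because the study is descriptive.

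**2. How many people the rule could touch.** Leavers aged 80 or over = n × d:
- n = 35: 3.5 to 7 leave, 31.5 to 28 remain
- n = 40: 4 to 8 leave, 36 to 32 remain

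This is about 4 to 8 people, or roughly 5-11% of the 65-70 enrolled (3.5/65 = 5.4%; 8/70 = 11.4%). It is a count over the roughly 18 months of the study.

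**3. How a day 31 titre can be lost.**
- *Through 6.3.* The primary analysis runs once all day 31 samples are in. The people exposed at that point are those who leave after their own day 31 sample and before that analysis. Later leavers are exposed only if the day 31 data are analysed again. The documents give no timing of drop-out, so this number cannot be derived; it is at most the count in step 2.
- *Through the per-protocol definition.* Taken literally, it removes every leaver, consenting or not. It also cannot be applied when the primary analysis is due, because trial completion then lies about 17 months ahead (18 months less one).

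Changing 6.3 alone would therefore not keep leavers in the primary analysis. Changing the per-protocol definition alone would leave the consent condition in force for the all-vaccinated and safety analyses.

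**4. Possible effect on the GMT (assumed values; the documents give no SD and no titre difference).** If a fraction d leaves and leavers' true GMT is lower than completers' by a factor r, then log GMT(all) = log GMT(completers) − d × log r. Dropping the leavers overstates the GMT by a factor r^d:

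| r | d = 0.10 | d = 0.20 |
|---|---|---|
| 1.5 | 1.04 | 1.08 |
| 2 | 1.07 | 1.15 |
| 3 | 1.12 | 1.25 |

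If leavers have higher titres, the same factors apply as understatement. For scale, with an assumed log10 SD of 0.3 to 0.5, the 95% confidence factor 10^(t × SD / √n) is 1.25 to 1.45 at n = 40 and 1.28 to 1.51 at n = 32.

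**5. Possible effect on a safety percentage (assumed counts).** Take 40 vaccinated, 8 leavers and 6 people with an SAE: 6/40 = 15.0% with all data. If the leavers' data are not used:
- 4 of the 6 are leavers: 2/32 = 6.3%
- 2 of the 6 are leavers: 4/32 = 12.5%
- none is a leaver: 6/32 = 18.8%

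The reported rate can move either way.

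**The case against.** The strongest reply is that the entry consent already governs. Section 6.3 speaks of consent that has been given; 12.3 requires signed consent before any trial-specific activity; 12.4 says participants are told how their data will be used. On that reading 6.3 is only loosely worded. This may be right, and it cannot be checked because the consent form is not in the documents at hand. But if the entry consent always covered this use, the proviso would do no work, and the permissive wording would remain.

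A reader might infer several stronger things that the documents do not support:
- *That consent is sought at discontinuation, so people who die or cannot be reached are lost.* Nothing says so. Section 6.3 foresees failed contact only for the follow-up visit.
- *That 4 to 8 day 31 titres are at risk through 6.3.* That is drop-out over the whole study.
- *That the older group's GMT would be biased upward and its event rates downward.* No passage says why people leave or how leavers respond.
- *That drop-out is expected only in the older group.* A rate is stated only there, which does not mean none is expected elsewhere.
- *That safety events would go unrecorded.* Section 9.3 has events registered whatever their causality, apart from the listed exclusions; fatal SAEs are recorded to study end, and 6.3 plans a safety visit after discontinuation. Only use in the analysis is left open.

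It is also fair to say that analysis sets usually belong in the SAP, that 10.2.2 promises to report the extent of missing data, and that the assumed GMT distortions are no larger than the sampling uncertainty. However, an SAP should not override a consent condition set by the protocol, and reporting how much is missing does not prevent avoidable exclusion.

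**Conclusion.** The point holds in a limited form. Section 6.3 makes analysis of leavers' existing data discretionary and conditional on an undefined consent, which does not fit the opening aim of 10.1, its all-vaccinated set or the safety percentages by age group. The text allows selective exclusion; it does not plan it. The per-protocol definition is a second route, and for the day 31 endpoint the broader one.

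The group exposed is about 4 to 8 of the 35-40 older participants over the whole study, assuming that the stated 10-20% drop-out occurs. Fewer are probably exposed for day 31 through 6.3. The direction of bias is unknown, and the sizes computed above rest on assumed values. The change is worth making because discontinuation can depend on adverse events, the trial is open-label, the older group is small and the repair costs very little.

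**What to change.** - **Section 6.3:** replace the sentence with: *Data and samples collected up to discontinuation will be included in all analyses for which the participant is evaluable, under the consent given at entry, unless the participant expressly refuses; refusals are reported by age group.* This also covers day 31 serum taken but not yet tested.
- **Consent information:** say the same. If the form already does, 6.3 then simply matches it.
- **Safety analysis:** state that it includes the recorded events of every vaccinated participant.
- **Section 10.1 and the abbreviation list:** define per-protocol for the day 31 endpoint by compliance up to day 31, not by completion of the trial.

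The cost is one replaced sentence, two short clarifications and matching consent wording, handled under section 13 if judged substantial. No new visits, samples or data are needed, and a participant's express refusal is still respected.

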## **7. Trial treatments**

### **7.1. Description of investigational medicinal product(s)**

Arexvy (manufactured by GSK) is a sterile injectable suspension for intramuscular use (8). The vaccine comes as a vial of lyophilized recombinant RSV glycoprotein F stabilized in pre-fusion conformation (RSVPreF3) as the antigen component, which must be reconstituted at the time of use with the accompanying vial of AS01E as the adjuvant suspension component. AS01E is composed of 3-O-desacyl-4'-monophosphoryl lipid A [MPL] from *Salmonella minnesota* and QS-21, a saponin purified from plant extract *Quillaja saponaria* Molina, combined in a liposomal formulation. The liposomes are composed of dioleoyl phosphatidylcholine (DOPC) and cholesterol in a phosphate-buffered saline solution containing disodium phosphate anhydrous, potassium dihydrogen phosphate, sodium chloride and water for injection. Each dose also contains trehalose, dipotassium phosphate and polysorbate 80 as formulation excipients.

#### **7.1.1. Dose and administration**

Two doses of the EMA-approved study vaccine (Arexvy, 0.5mL, intramuscular) will be administered 12 months apart. Vaccine preparation and administration will be done by authorized medical personnel who will not participate in any of the study clinical evaluation assays. Vaccination will be performed under medical

supervision.

#### ***7.1.2. Packaging, labelling, and handling of investigational medicinal product(s)***

Arexvy is procured via a medicinal product vendor and therefore labelled and packaged as commercially available. The integrity of the cold chain for vaccine storage will be maintained through temperature logs during transportation and continuous monitoring of refrigerators used for vaccine storage. Site staff will be trained in proper procedures for vaccine handling, including the safe disposal of vaccines when necessary.

#### ***7.1.3. Drug Accountability and treatment compliance***

The clinical sites will maintain an inventory log to track the receipt, storage and use of the vaccines. The lot number, expiration date and condition of the vials upon arrival will be documented.

#### ***7.1.4. Randomisation***

This is an open label study, and no randomisation will be performed. Participants are included, and allocated to the respective age group, consecutively as they are found to be eligible for inclusion in the trial. If a participant discontinues their participation, the participant's trial-specific code will not be reused, and the participant will not be allowed to re-enter the trial again. In this trial, no replacement will be recruited for any participant that discontinues their participation in the trial.

#### ***7.1.5. Blinding***

This is an open trial, however each participant who consents to participate in the study will be assigned a unique identification number. This number will be used

to label all study-related data and biological samples to ensure confidentiality. Laboratory testing in this trial will be partially blinded. For laboratory tests carried out by GSK laboratories, data will be collected in an observer-blind manner, only the sample ID and date of the sampling will be made available. The laboratory in charge of the sample testing will be blinded to the intervention assignment. Codes will be used to link the participant and study (without any link to the intervention attributed to the participant) to each sample.

The sponsor's lab personnel will be aware of the specific site in which a sample was obtained and thereby also have knowledge about the respective allocation in an age group.

